11.4 Day 1 (\pm 2 days) of Cycle 2 and Beyond

The following procedures are to be performed:

- Record subject weight and temperature
- ECOG performance status
- Symptom based physical examination
- Hematology
- Chemistry (fasting not required)
- Pregnancy test (serum or urine) for females of child-bearing potential only
- [REDACTED]
- Concomitant medications
- Assessment of adverse events

In addition to the above procedures, the clinical site will conduct a drug accountability on the returned empty bottles and unused medications.

Allowances of \pm 2 days will be permitted on the date of the Day 1 of Cycle 2 and beyond visit in cases of scheduling conflicts or for convenience.

11.5 Day 22 (\pm 5 days) of Cycles 2, 4 and 6 and Cycles 9, 12, 15, etc.

The following procedures are to be performed:

- Review of adverse events and concomitant medications
- Tumor assessments will be conducted as in the screening visit.
 - Tumor assessment including radiological assessment should maintain actual time schedule regardless of treatment delays or interruptions. In other words, subjects

should have their tumor assessed approximately every 8 weeks from starting tipifarnib treatment through the first 6 months of study participation. Thereafter, the tumor assessment is to be performed approximately every 12 weeks. The frequency of tumor assessment (every 8 or 12 weeks depending on duration of study participation) is to be maintained regardless of the subject's treatment cycle.

- For the purposes of tumor assessment recording, the nomenclature Cycle 2 Day 22, Cycle 4 Day 22, Cycle 6 Day 22, Cycle 9 Day 22, Cycle 12 Day 22, etc. is used to name the tumor assessment visits. However, due to treatment delays or interruptions, it may happen that the tumor assessment visit will not coincide with the current treatment cycle for a given subject.

11.6 End of Treatment Visit

The following assessments will occur approximately 30 days (\pm 7 days) after the last administration of study drug or immediately before the administration of another anti-cancer drug, whichever takes place first:

Complete physical examination. Record subject weight and temperature. Record weight, temperature and other physical examination parameters as AE if they meet AE criteria.

- ECOG performance status.
- 12-lead ECG
- Hematology
- Coagulation
- Chemistry (fasting not required)
- Pregnancy test (serum or urine) for females of child-bearing potential only
- Circulating biomarkers samples (one plasma, one serum)
- Tumor assessments for subjects who have not previously demonstrated disease progression in the study unless completed within the previous 8 weeks.
- Assessments of adverse event and concomitant medications.
- Conduct drug accountability on the returned empty bottles and unused medications.

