8. As part of screening, appropriate PET-CT or spiral CT scans will be conducted within 28 days prior to dosing. In subjects with FDG avid lymphomas, PET-CT is the preferred scanning method for screening and all subsequent tumor assessments (Cycle 2, Cycle 4, Cycle 6, etc.). In subjects with low or variable FDG avid lymphomas, Spiral CT with contrast is the preferred scanning method for screening and all subsequent tumor assessments (Cycle 2, Cycle 4, Cycle 6, etc.). Subjects with contrast allergy may use non-contrast CT or MRI, whichever is required to adequately assess all disease. The same method of imaging must be used throughout a subject's participation on this study. Tumor assessments will also be conducted on Day 22 ± 5 days of Cycles 2, 4, 6 and every approximately 12 weeks thereafter (Cycles 9, 12, 15, etc.) until disease progression. Assessments at the End of Treatment visit will be performed if not done within the prior 8 weeks unless additional anticancer therapy has been initiated. Subjects who discontinue treatment for reasons other than disease progression should continue tumor assessments until disease progression or withdrawal of subject's consent. The imaging schedule (approximately every 8 weeks during the subject's first 6 months on study, thereafter every 12 weeks) should be maintained regardless of dosing delays or additional imaging assessments performed. Tumor scans will be reviewed by the clinical sites. Bone marrow assessment (biopsy or PET) will be performed at screening within 28 days of Cycle 1 Day 1. If baseline bone marrow assessment (biopsy or PET) was positive for lymphoma, a bone marrow biopsy or negative PET scan is mandatory to confirm a complete response.
9. Tipifarnib will be administered at a starting dose of 300 mg, orally with food, bid on days 1-21 of 28 day treatment cycles. Subjects who received tipifarnib bid on Days 1 – 7 and Days 15 – 21 during the conduct of earlier versions of this protocol may remain on that dose regimen at the discretion of the investigator. Alternatively, the subject may transition to receive a dose of 300 mg, orally with food, bid on days 1-21 of 28 day treatment cycles beginning on Day 1 of their next cycle.
10. An End of Treatment visit will be conducted within 30 days (± 7 days) from the last dose of tipifarnib or immediately before the initiation of any other anticancer therapy.

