Tumor assessments will be performed at screening, at the Day 22 visit (\pm 5 days) performed during Cycles 2, 4, 6 and once every approximately 12 weeks (cycles 9, 12, 15, etc.) thereafter, until disease progression. Tumor assessments will be performed more frequently if deemed necessary by the investigator. A tumor assessment will be performed upon treatment discontinuation (End of Treatment visit) if the reason for discontinuation is other than disease progression and no tumor assessment was performed in the prior 8 weeks. Subjects who discontinue treatment for reasons other than disease progression must continue tumor assessments until disease progression, withdrawal of subject's consent or initiation of another anticancer therapy. Determination of objective tumor response will be performed by the Investigator according to the Lugano Classification and/or mSWAT criteria. Subjects who have experienced a complete response may be considered for transplantation.

Efforts will be made to collect information on the subject's response and duration of response to the last prior therapy.

Upon disease progression, all subjects will be followed approximately every 12 weeks for survival and the use of subsequent therapy until either death or 12 months after accrual of the last study subject, whichever occurs first. Information on survival and subsequent anticancer therapy may be collected by phone.

All subjects will be followed-up for safety during treatment and up to approximately 30 days (+/- 7 days) after treatment discontinuation or until immediately before the initiation of another anti-cancer therapy, whichever occurs first. Additional follow up may be implemented until the subject recovers from any emergent treatment related toxicity or the adverse event is considered irreversible by the investigator. Target organ toxicities will be monitored via clinical and laboratory assessments using the National Cancer Institute Common Terminology Criteria for Adverse Events version 4.03 (CTCAE v 4.03).

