10.1 Efficacy Variables

Radiological and/or physical assessments of the tumor lesions will be made at screening (4 weeks before the first study drug administration) and at regular intervals as indicated in the schedule of activities (Table 1). Additional tumor assessments may be conducted at the judgment of the investigator. The imaging schedule (approximately every 8 weeks during the subject's first 6 months on study, thereafter every 12 weeks) should be maintained regardless of dosing delays or additional imaging assessments performed. Subjects who discontinue treatment for reasons other than disease progression must continue tumor assessments until disease progression, withdrawal of their consent to study procedures or initiation of another anticancer therapy. Efficacy assessments may also be conducted at treatment discontinuation (End of Treatment visit) if the reason for the treatment termination is other than disease progression and a tumor assessment was not done within 8 weeks before treatment discontinuation (assessment must be conducted before additional anti-tumor therapy is started). Scans at the End of Treatment visit will be also conducted if required to confirm response to treatment.

Lesions to be included in the tumor assessments should follow the Lugano Classification criteria and/or mSWAT. In subjects with FDG avid lymphomas, PET-CT is the preferred scanning method for screening and all subsequent tumor assessments (Cycle 2, Cycle 4, Cycle 6, etc.). In subjects with low or variable FDG avid lymphomas, Spiral CT with contrast is the preferred scanning method for screening and all subsequent tumor assessments (Cycle 2, Cycle 4, Cycle 6, etc.). Subjects with contrast allergy may use non-contrast CT or MRI, whichever is required to adequately assess all disease. The same method of imaging must be used throughout a subject's participation on this study.

Bone marrow assessment (biopsy or PET assessment) will be performed at screening within 28 days of Cycle 1 day 1. If baseline bone marrow assessment was positive for lymphoma, a bone marrow biopsy or PET evaluation would be mandatory to confirm a complete response (i.e. after radiographic assessment).

Objective response (complete response and partial response) as determined by the subject's best tumor response, duration of response, and time to progression will be assessed using the Lugano Classification and/or mSWAT.

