5. ANALYSIS POPULATIONS

Full Analysis Set (FAS)

FAS will include the data on study participants who received at least one dose of tipifarnib and had at least one post-dose disease response assessment.

[REDACTED]

[REDACTED]

All Subjects as Treated (ASaT) Population

The ASaT population consists of all enrolled subjects who received at least one dose of tipifarnib and have at least one post-dose safety assessment (any laboratory, vital sign, or other safety assessment).

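### The 8-week waiver of the End of Treatment scan is not limited to post-dose scans, so the screening scan can excuse the last required scan in some subjects who stop early and switch therapy

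*Protocol*

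**What the plan says.** The waiver is stated four times in the protocol.

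- Section 11.6, EOT visit: "Tumor assessments for subjects who have not previously demonstrated disease progression in the study unless completed within the previous 8 weeks".
- Synopsis, Table 1 footnote 8: "Assessments at the End of Treatment visit will be performed if not done within the prior 8 weeks unless additional anticancer therapy has been initiated".
- Section 8.1: a scan is made on stopping for a reason other than progression if "no tumor assessment was performed in the prior 8 weeks". SAP 3.1 repeats this rule.
- Section 10.1: a scan may be made if "a tumor assessment was not done within 8 weeks before treatment discontinuation", and it must come before any new anti-tumor therapy.

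None of these limits the qualifying assessment to one made after the first dose. Section 8.1 itself treats the baseline scan as a tumor assessment: "Tumor assessments will be performed at screening, at the Day 22 visit". Footnote 8 sets its timing: "appropriate PET-CT or spiral CT scans will be conducted within 28 days prior to dosing".

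The 8 weeks do not have one starting point. Section 10.1 counts back from treatment discontinuation, and Section 11.6 and footnote 8 from the EOT visit. Section 8.1 can be read either way.

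On the analysis side, SAP 5 admits to the FAS only treated subjects who "had at least one post-dose disease response assessment", and Protocol 12.1.1 is equivalent on this point. SAP 8.1 divides responders by the number in the FAS, and SAP 6.4 imputes nothing in the primary analysis. Protocol 8.2 does not list subjects without a post-dose scan among those to be replaced.

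**The concern.** A subject who stops before the first on-study scan has only the screening scan on file. If that scan satisfies the waiver, the site may properly omit the EOT scan, although it could be the only post-dose assessment the subject ever has. Without one, the subject is outside the FAS and leaves the ORR denominator altogether, instead of counting as a non-responder.

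The subjects exposed are those who stop within the first weeks, for example for toxicity or deterioration without documented progression, and move quickly to another treatment. Few are likely to be responders, so losing them would push the ORR upward. Missing scans of this kind cannot be recovered at the analysis stage.

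**Working it through.** **Inputs**

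- s = days from the screening scan to Cycle 1 Day 1; at most 28 (footnote 8).
- L = study day of last dose, with Cycle 1 Day 1 as Day 1.
- g = days from last dose to the EOT visit: 30 ± 7, or shorter if another anticancer drug is about to start (Section 11.6).
- Waiver length: 8 weeks = 56 days.
- First on-study scan: Cycle 2 Day 22 = 28 + 22 = Day 50, window Day 45 to 55.

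**Condition.** The time from screening scan to EOT visit is s + (L − 1) + g. The screening scan satisfies the waiver when

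s + (L − 1) + g ≤ 56, that is, L ≤ 57 − s − g.

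**Latest last-dose day at which the screening scan excuses the EOT scan**

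| Gap g | s = 1 | s = 14 | s = 28 |
|---|---|---|---|
| 30 days (standard visit) | Day 26 | Day 13 | never |
| 23 days (early edge of window) | Day 33 | Day 20 | Day 6 |
| 37 days (late edge of window) | Day 19 | Day 6 | never |
| 7 days (assumed, new therapy pending) | Day 49 | Day 36 | Day 22 |
| 0 days (Section 10.1 count, taking last dose as discontinuation) | Day 56 | Day 43 | Day 29 |

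The starting point matters. For a scan 28 days before dosing, the limit moves from never (standard EOT visit) to Day 29 (discontinuation).

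**Example.** Take s = 14 and a last dose on Day 21.

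- Standard visit: 14 + 20 + 30 = 64 days, which exceeds 56. The scan is required.
- Visit brought forward to 7 days by new therapy: 14 + 20 + 7 = 41 days. The scan is waived at a visit on Day 28. Under Sections 8.1 and 10.1, new therapy then ends the duty to scan, so the Day 50 scan is not required either.

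**Size.** Protocol 5.2 gives the only counts. Its response rates reproduce: 5/12 = 41.7% in the PTCL (CXCL12+) expansion cohort and 5/11 = 45.5% in the AITL cohort (printed as 45.4%). Not evaluable were 15 − 12 = 3 of 15 and 16 − 11 = 5 of 16. If every one of them were a non-responder and were counted, the rates would be 5/15 = 33.3% and 5/16 = 31.3%. Adding back a single AITL subject as a non-responder gives 5/12 = 41.7%. The full shifts are upper bounds for non-evaluability from any cause. They do not estimate the effect of the waiver.

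**The case against.** The strongest reply is that scanning does not stop with treatment. The Synopsis and Sections 8.1 and 10.1 oblige subjects who stop for reasons other than progression to go on being scanned. Sections 10.1 and 11.5 hold scans to the calendar, about every 8 weeks from the start of tipifarnib, whatever happens to dosing. A subject who stops on Day 21 is therefore still due a scan near Day 50, about when a standard EOT visit would fall (21 + 30 = Day 51). This stands. A reader might infer that the waiver by itself removes subjects from the FAS, and it does not. A second event is needed: new therapy, consent withdrawal, death or loss to follow-up before about Day 50.

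The reply fails for the switch to new therapy. In Sections 8.1 and 10.1 that event ends the scanning duty, and in Section 11.6 it also brings the EOT visit forward, which makes the waiver easier to meet. Footnote 8 and Section 11.7 do not name new therapy as an end to scanning, so the protocol is not uniform on this either.

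Three other inferences are tempting, and the documents do not support them.

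- That every subject who stops before the first on-study scan is exempt. At a standard 30-day visit most of that period is not covered, and with a scan 28 days before dosing none of it is.
- That the 8 of 31 non-evaluable expansion subjects show the waiver at work. The report was preliminary and gives no reasons; some may only have been awaiting a scan.
- That PFS is biased upward. Under SAP 8.2 a subject recovered with a non-progression EOT scan and no later progression or qualifying death would be censored at that scan, so the effect on the median may be small.

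The proposed rewording also does nothing for subjects who die or are lost before the EOT visit.

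**Conclusion.** The gap is real but narrow. Read literally, a pre-dose scan can excuse the EOT scan in some subjects who stop before Day 50. It matters mainly for those who start another anticancer therapy before then, because the EOT visit is their last required chance for a post-dose assessment. Such a subject falls out of the FAS and the ORR denominator. The likely direction is upward for ORR, assuming that these subjects are mostly non-responders; an effect on PFS is not established.

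How many subjects are affected is unknown, and the documents identify none. In the AITL cohort, 45% to 31% is a ceiling for all causes of non-evaluability together. The day limits rest on the stated visit windows; only the 7-day gap is an assumption. The two starting points for the 8 weeks are a separate inconsistency that changes who is exempt.

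**What to change.** In Protocol Sections 8.1, 10.1 and 11.6 and Table 1 footnote 8, and to match in SAP 3.1, word the waiver as: *unless a post-baseline tumor assessment was completed within the previous 8 weeks*. Reconcile the starting point of the 8 weeks across these places, and keep the existing requirement in Section 10.1 that the scan come before new therapy. State uniformly whether new therapy ends tumor follow-up.

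The cost is a few words in five places, and an EOT scan, already in the schedule, that is actually performed in a few early stoppers.

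Rewording cannot recover scans in subjects already treated. For them, the clinical study report should give the number without a post-dose assessment, whether the EOT scan was waived on the strength of the screening scan, and a sensitivity ORR with all treated subjects in the denominator and those without a post-dose assessment counted as non-responders. This needs no new data beyond scan, dosing and visit dates.

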11.7 Post Treatment Follow up

If the reason for the discontinuation was other than disease progression, tumor assessments will continue to be performed after treatment discontinuation in approximately 8-12 week intervals until progression.

Tumor assessments to be conducted at these visits. Assessments of adverse events and concomitant medications may also be conducted if adverse events were not resolved at the time of the End of Treatment visit.

In subjects who have experienced a response and in whom only residual tumor tissue remains, irradiation of the remaining tumor lesions will be permitted as per standard of care.

11.7.1 Follow Up after Disease Progression

Upon disease progression, all subjects will be followed approximately every 12 weeks for survival and the use of subsequent therapy until either death or 12 months after accrual of the last study subject, whichever occurs first. Information on survival and subsequent anticancer therapy may be collected by phone.

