Tumor assessments will be performed at screening, at the Day 22 visit (\pm 5 days) performed during Cycles 2, 4, 6 and once every approximately 12 weeks (cycles 9, 12, 15, etc.) thereafter, until disease progression. Additional tumor assessments may be conducted if deemed necessary by the Investigator. Subjects who discontinue tipifarnib treatment for reasons other than disease progression must continue tumor assessments until disease progression, withdrawal of subject's consent to study procedures or initiation of another anticancer therapy.

Determination of objective tumor response will be performed based on the Lugano Classification (Cheson 2014, [Appendix II: The Lugano Classification](#)) and/or measurable cutaneous disease according to the modified Severity Weighted Assessment Tool (mSWAT, Olsen 2011, [Appendix III: Modified Severity Weighted Assessment Tool](#)). Subjects who have experienced a complete response may be considered for transplantation. Information on this intervention and other subsequent anti-cancer therapies will be collected for these subjects.

Upon disease progression, subjects will be followed approximately every 12 weeks for survival until either death or 12 months after accrual of the last study subject, whichever occurs first. Information on subsequent anticancer therapy will be collected.

All subjects will be followed-up for safety during treatment and for approximately 30 additional days after treatment discontinuation (or until immediately before the administration of another anticancer treatment). Additional safety follow up may be conducted if unresolved toxicity is present at the End of Treatment visit.

NUMBER OF SUBJECTS PLANNED: Up to 70 study subjects.

SUBJECT SELECTION:

Inclusion Criteria

For inclusion of a subject in the study, all of the following inclusion criteria must be fulfilled:

1. Subject is at least 18 years of age.
2. Subject has a diagnosis of PTCL according to the most recent edition of the World Health Organization (WHO) Classification of Tumors of Hematopoietic or Lymphoid Tissues as follows:
 - a. Anaplastic large cell lymphoma (ALCL), ALK positive
 - b. ALCL, ALK negative
 - c. Angioimmunoblastic T-cell lymphoma (AITL)
 - d. Enteropathy-associated T-cell lymphoma
 - e. Extranodal natural killer (NK) T-cell lymphoma, nasal type
 - f. Hepatosplenic T-cell lymphoma

- g. Peripheral T-cell lymphoma, no otherwise specified (NOS)
- h. Subcutaneous panniculitis-like T-cell lymphoma

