8.3. Exploratory Efficacy Analysis

Exploratory analysis will be conducted as deemed appropriate. It will include sensitivity analysis described in Section 8.1 and Section 8.2. Exploratory analysis can be based on either or both FAS [REDACTED] data sets.

An analysis of overall survival to estimate median overall survival time and corresponding 95% confidence interval and provide per subject summary of overall survival will be conducted overall and for each subtype (AITL, PTCL-NOS, CXCL12+, and Other). Overall survival will be defined as the time (in months) from first dose (Cycle 1 Day 1) to the occurrence of death due to any cause. In subjects without a death date, the OS will be censored on 1) the date a subject has end of study reason of 'ended study per protocol' for subjects with no survival status documentation, or 2) the date a subject withdraws consent from study or is lost to follow-up, if there is no additional information. Subjects who ended study per protocol were no longer followed for survival status.

ORR, PFS, and DOR will be evaluated in the subgroups of partial and complete responders. Further analysis may be conducted to evaluate the impact of age, disease duration and severity, IPI scores, geography, and other potentially influential covariates on ORR, PFS, and DOR. This analysis will be conducted using parametric models – logistic for ORR and Cox-regression for PFS and DOR.

Tumor data may be analyzed using longitudinal mixed-effect models. Models will be explored to include covariates that can affect the tumor dynamics. Tumor data will also undergo subgroup analysis in AITL, PTCL-NOS, CXCL12+, and Other sub-populations. The analysis will be visualized using model summary plots, waterfall plots for maximum reduction in tumor lesion size, and spider plots to depict the reduction in tumor lesion by subject for the FAS [REDACTED] populations.

Biomarkers will be listed and may be further analyzed outside of this report.

Exploratory analysis may also include sensitivity analysis to the statistical methodology and stability analysis when a small sample is present.

Other exploratory analysis can be conducted as deemed appropriate.

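### The stopping rules for tumour assessments conflict, and under one of them subjects who start new therapy or go to transplant before progression have no scheduled survival contact

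*Protocol*

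**What the plan says.** **Survival contact.** Protocol 11.7.1: "Upon disease progression, all subjects will be followed approximately every 12 weeks for survival and the use of subsequent therapy", until death or 12 months after the last subject is accrued. The Synopsis has the same trigger ("Upon disease progression, subjects will be followed approximately every 12 weeks for survival"), as do Protocol 8.1 and 10.1, Table 1 footnote 12 and SAP 3.1.

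**Tumour assessments after stopping treatment without progression.** There are two rules.
- *Stop at new therapy.* Protocol 8.1: subjects "must continue tumor assessments until disease progression, withdrawal of subject's consent or initiation of another anticancer therapy". The Synopsis text, Protocol 10.1 and SAP 3.1 agree.
- *Scan to progression.* Table 1 footnote 8: subjects "should continue tumor assessments until disease progression or withdrawal of subject's consent". Protocol 11.7: "tumor assessments will continue to be performed after treatment discontinuation in approximately 8-12 week intervals until progression". Footnote 19 agrees with 11.7. None of the three lists new therapy as a stop.

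**Transplant.** The Synopsis says: "Subjects who have experienced a complete response may be considered for transplantation". Its next sentence counts transplant among later anticancer treatments and promises information on them. It gives no schedule and does not name survival.

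**Analyses.** SAP 8.2 counts a death as a PFS event if it falls within 126 days of the last treatment or assessment, and otherwise censors at the last evaluable assessment. It has no rule for new therapy. SAP 8.3 plans an exploratory OS analysis, overall and by subtype.

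**The concern.** The survival trigger is a progression. Under the stop-at-new-therapy rule, nobody is scheduled to look for progression once a subject has switched, so the trigger may never be reached. Those affected are selected by outcome: complete responders fit enough for transplant, and subjects who leave for toxicity and start something else. If their vital status becomes unknown at that point, censoring may be related to prognosis.

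Separately, two sites can follow the same protocol and produce different PFS data for the same clinical course. PFS is a secondary endpoint and the SAP does not say how to treat the difference.

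**Working it through.** The plan states no figure on this point, so the check is mainly a reading of the passages side by side, followed by a count of the exposed group.

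**Step 1. Trace one subject.** Take a subject who stops tipifarnib without progression and then starts another therapy or goes to transplant.

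| | Stop at new therapy | Scan to progression |
|---|---|---|
| Where stated | Synopsis text, Protocol 8.1, 10.1, SAP 3.1 | Table 1 fn 8 and 19, Protocol 11.7 |
| Scans after the switch | none scheduled | every 8 to 12 weeks under 11.7 |
| Survival contact | opens at a progression no longer looked for | opens at the progression found |
| Result | no scheduled contact | follow-up continues |

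The Synopsis contains both rules, one in its text and the other in its table footnotes.

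**Step 2. Look for any other contact under the first rule.**
- Adverse event reporting closes at 30 days or just before other anticancer therapy, whichever is first (Protocol 10.9).
- The End of Treatment visit falls no later than the start of the new drug (11.6).
- A subject who needs a non-permitted drug is withdrawn from the trial (9.12).
- The Table 1 row for survival and treatment information has two marks. The columns are uncertain in the extracted text, but one may be the Follow Up Visit. Footnote 19 makes that visit a tumour-assessment visit, so under this rule it also ends at new therapy.

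No scheduled contact remains.

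**Step 3. Follow the subject into the analyses.**
- *PFS, death after a switch.* Suppose death occurs within 126 days of the last assessment. If the death is known, it is an event. If not, the subject is censored at that last assessment.
- *PFS, progression after a switch.* Where scanning continues, progression under the new therapy enters as an event at its date. Where scanning stops, the subject is censored at the last scan before the switch. Both kinds of record enter one Kaplan-Meier curve.
- *Duration of response.* Protocol 12.2.1 censors at non-protocol therapy. SAP 8.2 omits that rule and SAP 14 does not list the change.
- *OS.* SAP 8.3 censors subjects without a death date at per-protocol end of study, consent withdrawal or loss to follow-up.
- *Objective response rate.* This gap does not affect it.

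**Step 4. Size of the group exposed through transplant.** The inputs are from Protocol 5.2.
- CXCL12+ cohort: 3 complete and 2 partial responses in 12 evaluable. Check: 5/12 = 41.7%, as stated.
- AITL expansion cohort: 3 complete and 2 partial responses in 11 evaluable. Check: 5/11 = 45.45%, stated as 45.4%.
- Complete responders: (3 + 3)/(12 + 11) = 6/23 = 26.1%. The exact 95% limits are the 2.5% quantile of Beta(6, 18) and the 97.5% quantile of Beta(7, 17), which give 10% to 48%.

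The documents do not say how many were transplanted. With 0 to 6 transplanted, the share is 0/23 to 6/23, or 0% to 26%. If one assumes that 10% to 50% of complete responders go to transplant, the count is 0.6 to 3 subjects, or 0.6/23 = 3% to 3/23 = 13%. Subjects who switch drug before progression come on top, and no figure is given for them.

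**The case against.** The strongest reply is that a reader might infer that these subjects leave both tumour and survival follow-up under the protocol as a whole. The documents do not support that. Footnotes 8 and 19 and Protocol 11.7, which directly precedes the survival section, keep them in tumour follow-up until progression and so bring them into survival contact. The gap exists under one of two conflicting rules. This stands.

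Four further points also have weight.
- *Survival may be collected before progression.* The Table 1 row may place it at the Follow Up Visit. This holds for subjects still being scanned, but it does not help switchers once that visit has ended.
- *The subjects are not missing from OS.* They contribute time until they are censored. The sentence "Subjects who ended study per protocol were no longer followed for survival status" concerns subjects who ended the study per protocol and does not mention transplant or new therapy. The valid worry is that the censoring may be informative.
- *Some PFS text already exists.* Protocol 12.2.1 says PFS should take account of assessments after treatment discontinuation or metastatic surgery, and SAP 8.2 allows sensitivity analyses of censoring. Neither is a rule for new therapy, and the SAP analyses are optional.
- *The 26% is a ceiling.* It requires every complete responder to be transplanted, and the Synopsis says only that transplant may be considered. It measures exposure and not bias.

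**Conclusion.** The point holds as a conflict between follow-up rules. Under the rule in the Synopsis text, Protocol 8.1 and 10.1 and SAP 3.1, a subject who starts new therapy or is transplanted before progression has no scheduled survival contact. Under the other rule the subject stays in follow-up.

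The consequences are possible informative censoring in the exploratory OS, possible missed deaths in the 126-day PFS window, and secondary PFS data that depend on the rule a site applied. It would be wrong to read this as a threat to the primary response rate or as evidence that a quarter of subjects were lost.

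The exposed share through transplant is 0% to 26% of the 23 evaluable expansion-cohort subjects, plus an unstated number of other switchers. This rests on transplant counting as another anticancer therapy, as the Synopsis wording implies, and on the preliminary response counts in Protocol 5.2. The direction and size of any bias cannot be derived from the documents.

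**What to change.** 1. **Reconcile the tumour-assessment stop rule** so that it reads the same in the Synopsis, Protocol 8.1, 10.1 and 11.7, Table 1 footnotes 8 and 19, and SAP 3.1.
2. **Widen the survival trigger.** In the Synopsis, Protocol 8.1, 10.1 and 11.7.1, Table 1 footnote 12 and SAP 3.1, start the existing 12-weekly survival and subsequent-therapy contact at progression or at the start of another anticancer therapy (transplant included), whichever is first.
3. **State the PFS rule.** In SAP 8.2, before database lock, say how scans and deaths after new therapy enter PFS. Report PFS both with them included and with censoring at the last assessment before new therapy.

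The cost is amended wording, a few extra phone contacts on a schedule that already exists (11.7.1 allows the phone), and one extra PFS analysis. No new visits or procedures are needed. The SAP cites a January 2021 brochure and describes subjects already enrolled. If follow-up has closed, added contacts may recover nothing and only item 3 remains feasible.
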